4.2. Measures Taken to Avoid Bias

This is an open-label study. Assessment of safety using CTCAE v4.03 and efficacy using RECIST v1.1 and mRECIST v1.1 are objective measurements, and only comparisons to pretreatment conditions will be made.

4.3. Number of Subjects

4.3.1. Planned Number of Subjects

Approximately 384 to 1039 subjects may be enrolled as follows:

- Phase 1 Dose Escalation – Approximately 90 to 270 evaluable subjects.
Note: The minimum number of subjects assumes that the starting dose is 0.1 mg/kg; however, fewer subjects would be enrolled if a higher starting dose is used based on available safety data from the monotherapy study INCAGN 1876-101.
Note: The maximum number of subjects assumes that DLTs are observed in all dose cohorts to a maximum of 9 subjects per cohort across all treatment groups.
- Phase 2 Stage 1 – Approximately 264 evaluable subjects.
- [REDACTED]
- Phase 2 Stage 2 – Approximately 455 evaluable subjects.
- Phase 2 Expansion Stage (PD-1 refractory SCCHN cohort only) – Approximately 20 evaluable subjects
Note: Assumes that all treatment groups and all tumor types proceed to Stage 2 and Expansion Stage (for PD-1 refractory SCCHN cohort only).

4.3.2. Replacement of Subjects

Subjects may be replaced for any of the following reasons:

- In Phase 1, any subject who withdraws from treatment before the completion of the DLT observation period for any reason other than a DLT (ie, is not evaluable for DLTs; see Section 5.4.2), may be replaced to ensure a minimum number of evaluable subjects.
- [REDACTED]
- Subjects who do not meet the eligibility requirements of the study may be replaced.

Subjects who meet any of the criteria for replacement may remain on study for evaluation as outlined in Section 9.1 and Section 9.2.

4.4. Duration of Treatment and Subject Participation

After signing the ICF, screening assessments may be completed over a period of up to 28 days. Subjects may continue to receive study treatment as long as they are deriving benefit and have not met any of the Protocol-defined conditions for treatment withdrawal (see Section 5.5), or for

up to 24 months from the first dose of study treatment, whichever occurs first. If the subject discontinues study treatment, the treatment period will end and the subject will enter the follow-up period (see Section 6.4). Study participation, including post-treatment follow-up is expected to average approximately 12 to 18 months per individual subject.

4.5. Overall Study Duration

The study begins when the first subject signs the ICF. The end of the study will occur when all subjects have discontinued treatment and the last follow-up visit has been performed.

If there are ≤ 5 subjects on study for more than 6 months, a database lock of the study may occur to allow the analysis of the study data. Any remaining subjects may continue to receive study treatment and be seen by the investigator per usual standard of care for this population. The investigator will be expected to monitor for and report any AEs, SAEs, pregnancies, and deaths as detailed in Section 8 and Section 6.4.3. The remaining subjects are considered to be on study until a discontinuation criterion is met and written notification is provided to the sponsor.

4.6. Study Termination

The investigator retains the right to terminate study participation at any time, according to the terms specified in the study contract. The investigator is to notify the IRB/IEC in writing of the study's completion or early termination, send a copy of the notification to the sponsor or sponsor's designee, and retain 1 copy for the site study regulatory file.

The sponsor may terminate the study electively, if required by regulatory decision, or upon review of emerging data. If the study is terminated prematurely, the sponsor will notify the investigators, the IRBs and IECs, and regulatory bodies of the decision and reason for termination of the study.

5. TREATMENT

5.1. Treatment Assignment

5.1.1. Subject Numbering and Treatment Assignment

Each subject will be identified in the study by a subject ID number, which is a combination of the site ID and subject number. Site staff should contact the IRT to obtain the subject ID number and confirm a slot is available during prescreening. This subject ID number will be maintained throughout the study and will not be reassigned. Subjects who fail screening and are repeating the screening process due to a change in eligibility status will be assigned a new subject ID number. The site staff will contact the IRT to enroll the subject and obtain the study drug and treatment group assignment. All subsequent cycles will follow this process. The IRT will also be contacted for ordering study drug supplies and when subjects are discontinued from treatment. Full details will be provided in the IRT manual.

5.1.2. Randomization and Blinding

This is an open-label nonrandomized study; therefore, randomization and blinding do not apply.

5.2. Study Drugs

5.2.1. INCAGN01876

5.2.1.1. Description and Administration

The study drug (INCAGN01876) is supplied as a sterile, single-use solution for injection, in a 10 mL glass vial. Each vial contains 50 mg of INCAGN01876 in 5 mL at a concentration of 10 mg/mL in [REDACTED], and pH [REDACTED]. The infusion site should not be used for blood sampling.

Study drug will be diluted in [REDACTED] or acceptable admixture as outlined in the Pharmacy Manual and will be administered by qualified site personnel as an IV infusion over a 30-minute (-5/+10 minutes) period on Day 1 of each cycle when INCAGN01876 is scheduled to be given. On days when INCAGN01876 will be administered along with other agents administered by infusion, INCAGN01876 will be administered first, followed by a 30-minute wait before administration of the subsequent immune therapy/therapies.

In Phase 1, subjects will be administered study drug, according to cohort enrollment (see [Table 2](#)), Q2W (14-day cycles), in combination with immune therapies. In Phase 2, subjects will be administered study drug at the recommended dose Q2W (14-day cycles), in combination with immune therapies. In Treatment Group B, INCAGN01876 is only administered on Day 1 of Cycles 1 and 2.

Subjects will continue to receive INCAGN01876 as long as they are deriving benefit and have not met any of the Protocol-defined conditions for treatment withdrawal (see Section [5.5](#)), or for up to 24 months from the first dose of study treatment, whichever occurs first.

5.2.1.2. Supply, Packaging, and Labeling

Study drug will be supplied as a sterile, single-use solution for injection in 10 mL glass vials. Study drug will be packaged as open-labelled supplies; each vial will be labelled and placed in a carton. The Pharmacy Manual contains additional information regarding supply, packaging, and labeling of study drug.

The investigator shall take responsibility for and shall take all steps to maintain appropriate records and ensure appropriate supply, storage, handling, distribution, and usage of study drug in accordance with the Protocol and any applicable laws and regulations.

All Incyte investigational product labels will be in the local language and will comply with the legal requirements of each country.

5.2.1.3. INCAGN01876 Storage

Study drug must be stored refrigerated (2°C-8°C) and protected from light, in a secure, limited access location. Receipt and dispensing of study drug must be recorded by an authorized person at the study site. Study drug may not be used for any purpose other than that stated in the Protocol. The Pharmacy Manual contains additional information regarding storage of study drug.

5.2.2. Standard Immune Therapies

5.2.2.1. Nivolumab

Nivolumab will be administered IV per the package insert or institutional guidelines at the site, at a dose that is dependent on the assigned treatment group as follows:

- Doublet Treatment Groups A, B, F, and H: 240 mg on Day 1 of every 2-week (ie, 14-day) cycle.
- Triplet Treatment Groups D, E, J, and L: 3 mg/kg on Day 1 of every 2-week (ie, 14-day) cycle.
- Concurrent dosing Treatment Groups A, D, F, and J: Nivolumab dosing will begin on Cycle 1 Day 1.
- Sequenced dosing Treatment Groups B, E, H, and L: Nivolumab dosing will begin on Cycle 3 Day 1.

Nivolumab will be administered at least 30 minutes after the infusion of INCAGN01876 (when applicable), and subjects will continue to receive nivolumab as long as the subject is deriving benefit and has not met any of the Protocol-defined conditions for treatment withdrawal (see Section 5.5), or for up to 24 months from the first dose of study treatment, whichever occurs first.

Nivolumab is commercially available. Investigators are responsible for ensuring that subjects receive commercially available supplies of nivolumab for the entire duration of study participation. Incyte may provide certain standard of care medications such as nivolumab where required by applicable law or specific regulation or under other circumstances when subjects may not otherwise have access to them. Nivolumab must be used in accordance with the storage conditions and shelf life in the manufacturer's approved label.

5.2.2.2. Ipilimumab

Ipilimumab will be administered IV per the package insert or institutional guidelines at the site, at a dose that is dependent on the assigned treatment group as follows:

- Doublet Treatment Group C and C2 (Phase 2 Expansion) and Triplet Treatment Groups D, E, J, and L: 1 mg/kg on Day 1 of every 6-week (eg, 42-day) cycle.
- Concurrent dosing Treatment Groups C and C2 (Phase 2 Expansion), D, and J: Ipilimumab dosing will begin on Cycle 1 Day 1.
- Sequenced dosing Treatment Groups E and L: Ipilimumab dosing will begin on Cycle 3 Day 1.

Ipilimumab will be administered at least 30 minutes after the infusion of INCAGN01876 (when administered on the same day). Ipilimumab will always be administered after INCAGN0876 and nivolumab. Subjects will continue to receive ipilimumab as long as the subject is deriving benefit and has not met any of the Protocol-defined conditions for treatment withdrawal (see Section 5.5), or for up to 24 months from the first dose of study treatment, whichever occurs first.

At the sponsor's discretion, once the MTD or PAD of INCAGN01876 has been established with ipilimumab at 1 mg/kg Q6W, a higher dose of ipilimumab at 3 mg/kg Q6W and/or 3 mg/kg Q3W for 4 doses may be tested.

Ipilimumab is commercially available. Investigators are responsible for ensuring that subjects receive commercially available supplies of ipilimumab for the entire duration of study participation. Incyte may provide certain standard of care medications such as ipilimumab where required by applicable law or specific regulation or under other circumstances when subjects may not otherwise have access to them. Ipilimumab must be used in accordance with the storage conditions and shelf life in the manufacturer's approved label.

5.3. Treatment Compliance

5.3.1. Treatment Compliance of INCAGN01876, Nivolumab, and Ipilimumab

INCAGN01876, nivolumab, and ipilimumab are administered as an IV infusion by site personnel. Receipt of infusions will be documented by the site staff and monitored by the sponsor/designee.

5.4. Treatment Interruptions and Adjustments

5.4.1. Dose Modifications

Selections to the study drug (INCAGN01876) are planned for dose-escalation cohorts (see Section 4.1.1). Dose interruptions of study drug may also occur for individual study subjects. The identification of DLTs will define the doses used in planned cohorts (see Section 5.4.2). Further, the occurrence of DLTs and other toxicities (related or unrelated to study drug) will guide decisions for treatment interruptions and discontinuation for individual subjects. Intrasubject dose escalation will not be permitted.

No dose reductions of INCAGN01876 are allowed for the management of toxicities of individual subjects. Doses of INCAGN01876 may be delayed for toxicity management (see Section 5.4.6).

In the event of any significant treatment related adverse events, holding of the therapy or discontinuation as per Table 7 would be advised.

No dose reductions of nivolumab or ipilimumab are allowed for the management of toxicities of individual subjects. Doses of nivolumab and ipilimumab may be delayed for toxicity management (see Section 5.4.6). Nivolumab and ipilimumab are approved therapies and have specific subject safety management guidelines within their package insert; the treating investigator should refer to and follow the labeled guidance for both nivolumab and ipilimumab.

5.4.2. Dose-Limiting Toxicity and Determination of Maximum Tolerated Dose

The evaluation period for DLTs will begin on Cycle 1 Day 1 and will continue up to and including study Day 28 for subjects in Treatment Groups A, C, D, F, and J. In the sequenced dosing Treatment Groups B, E, H, and L, the evaluation period for DLTs will begin on Cycle 3 Day 1 (first administration of nivolumab or nivolumab/ipilimumab) and will continue up for 28 days, up to and including study Day 56. All DLTs will be assessed by the investigator using CTCAE v4.03 criteria. A DLT will be defined as the occurrence of any toxicity in Table 6, with the exception of events clearly associated with the underlying disease, disease progression, a concomitant medication, or comorbidity.

Decisions for dose cohort escalation/de-escalation, expanding a dose cohort, and determining the MTD of INCAGN01876 will be made based on events that are observed during the DLT evaluation period. A lower MTD may subsequently be determined based on relevant toxicities that become evident after the end of the DLT evaluation period.

Table 6: Definition of Dose-Limiting Toxicity

Nonhematologic toxicity

 • Any \geq Grade 3 nonhematologic toxicity EXCEPT the following: 
 – Transient (\leq 72 hours) abnormal laboratory values without associated clinically significant signs or symptoms. – Nausea, vomiting, and diarrhea adequately controlled with supportive care within 48 hours. – Changes in cholesterol and triglycerides. – An event clearly associated with the underlying disease, disease progression, a concomitant medication, or comorbidity. – Asymptomatic changes in amylase and lipase. – Single or nonfasting elevations in blood glucose (ie, blood glucose excursions will be considered toxicities if fasting blood glucose is elevated on 2 separate occasions). – Grade 3 rash in the absence of desquamation, with no mucosal involvement, that does not require systemic steroids, and that resolves to Grade 1 within 14 days.
Hematologic toxicity

 • Grade 3 thrombocytopenia with clinically significant bleeding (ie, requires hospitalization, transfusion of blood products, or other urgent medical intervention). • Grade 4 thrombocytopenia. • \geq Grade 3 febrile neutropenia (absolute neutrophil count $< 1.0 \times 10^9/L$ and fever $> 101^\circ F/38.3^\circ C$). • Grade 4 neutropenia that does not recover to \leq Grade 2 in ≤ 3 days after interrupting study treatment. • Grade 4 anemia not explained by underlying disease or some other concomitant disorder.
Immune-related toxicity^a

 • \geq Grade 2 ocular irAEs will be considered a DLT. • Grade 3 irAEs that do not improve to baseline or at least Grade 1 in < 5 days with appropriate care or with corticosteroid therapy will be considered a DLT. • Grade 4 irAEs will be considered a DLT regardless of duration.
General

 • Inability to receive the planned number of doses within the 28-day DLT period due to toxicity, regardless of grade, will be considered a DLT.
MTD

 • In Phase 1 of the study, the MTD will be defined as 1 dose level below that at which \geq one-third of subjects in a particular cohort have DLTs. • In Phase 2 of the study, toxicities will continue to be monitored. If the cumulative incidence of Grade 3 or higher INCAGN01876-related AEs occurs in $> 40\%$ of subjects in a particular treatment group after 6 subjects have been enrolled, then further enrollment in that treatment group will be interrupted until the sponsor, investigators, and regulatory authorities (if applicable) determine the appropriate course of action (eg, lower the dose of INCAGN01876, change dose frequency, etc). If a treatment group is discontinued due to toxicity, it may be re-initiated at a previously tested lower dose level and/or alternate dosing schedule. All AEs, regardless of the time of occurrence on study, may be considered for DLT determination purposes.

^a Immune-related AEs are a diagnosis of exclusion, after alternative etiologies have been ruled out.

5.4.3. Management of Dose-Limiting Toxicities or Other Urgent Situations

In all cases, investigators may employ any measures or concomitant medications, after discussion with the medical monitor (whenever possible), necessary to optimally treat the subject.

5.4.4. Follow-Up of Dose-Limiting Toxicities

Any DLT should be followed until it resolves to baseline or appears to have stabilized for a minimum of 4 weeks (eg, 28 days). During follow-up, subjects should be seen as often as medically indicated to assure safety.

5.4.5. Procedures for Cohort Review and Dose Escalation

Telephone conferences will be scheduled by the sponsor with study investigators in order to review cohort-specific data and overall safety data, to agree on dose escalation, adjudicate individual high-grade AEs as potentially dose-limiting, and guide other major study decisions.

5.4.6. Criteria and Procedures for Dose Interruptions of Study Drug

Treatment with INCAGN01876 in combination with standard immune therapies may be delayed up to 4 weeks (28 days) to allow for resolution of toxicity. **If an interruption or discontinuation is necessary, all study treatments should be interrupted or discontinued.** Subjects may resume treatment if no medical condition or other circumstance exists that, in the opinion of the investigator, would make the subject unsuitable for further participation in the study. The treating investigator should contact the medical monitor to discuss the case of any subject whose treatment has been delayed for more than 4 weeks (28 days) before restarting treatment.

Instructions for INCAGN01876 dose interruptions are outlined in [Table 7](#). Individual decisions regarding dose interruptions of study drug should be made using clinical judgment and in consultation with the medical monitor (whenever possible), taking into account relatedness of the AE to the study drug and the subject's underlying condition. Adverse events that have a clear alternative explanation, or transient (≤ 72 hours) abnormal laboratory values without associated clinically significant signs or symptoms, may be exempt from dose-interruption rules.

Dose interruptions are permitted in the case of medical/surgical events or logistical reasons not related to study therapy (eg, elective surgery, unrelated medical events, subject vacation, and/or holidays). Subjects should be placed back on study therapy within 4 weeks (28 days) of the scheduled interruption, unless otherwise discussed with the medical monitor. The reason for interruption should be documented in the subject's study record.

Table 7: Criteria for Interruption and Restarting of Study Treatment

CTCAE Grade/Severity	Hold Treatment (Y/N)	Timing for Restarting Treatment	Dose Level for Restarting INCAGN01876	Dose Level for Restarting Immune Therapies	Treatment Discontinuation
1-2 (Mild-Moderate)	No	Continue treatment at the discretion of the investigator.	N/A	NA	N/A
3 (Severe)	Yes	Toxicity resolves to Grade 0-1.	Restart same dose	Restart same dose	Toxicity does not resolve within 4 weeks (28 days) of last dose, except by approval of the medical monitor. OR Second occurrence of previously resolved Grade 3 AE.
4 (Life-threatening)	Yes	Permanent discontinuation, except by approval of the medical monitor. If continuing, toxicity must resolve to Grade 0-1.	Permanent discontinuation, except by approval of the medical monitor. If continuing, restart same dose.	Permanent discontinuation, except by approval of the medical monitor. If continuing, restart same dose.	Permanent discontinuation for any severe or life-threatening event, except by approval of the medical monitor.

5.4.7. Management of Immune-Related Adverse Events

INCAGN01876, nivolumab, and ipilimumab are considered immune modulators, and it is possible that irAEs (both nonserious and serious) may occur. Adverse events of a potential immunologic etiology or irAEs may be defined as an AE consistent with an immune phenomenon associated with drug exposure *after all other etiologies have been eliminated*. Immune-related AEs may be expected based on the nature of the study treatment, their mechanism of action, and reported experience with these and other immunotherapies. Special attention should be paid to AEs that may be suggestive of potential irAEs. An irAE can occur shortly after the first dose or several months after the last dose of treatment. Suspected irAEs should be discussed with the medical monitor when possible.

Subjects should receive appropriate supportive care measures as deemed necessary by the treating investigator. Suggested supportive care measures for the management of drug-related AEs with potential immunologic etiology are outlined in [Table 8](#). Detailed supportive care guidelines for specific irAEs can be found in [Appendix B](#). Nivolumab and ipilimumab are approved therapies and have specific irAE management guidelines within their package insert; the treating investigator may use labeled guidance or institutional guidelines for the management of irAEs if preferred. For each AE, attempts should be made to rule out other causes, including but not limited to metastatic disease or bacterial or viral infection, which might require specific supportive care.

Table 8: Supportive Care Guidelines for Immune-Related Adverse Events

CTCAE Grade/Severity	Supportive Care ^a
Grade 1 (mild)	
 • Monitor symptoms and provide symptomatic treatment.
Grade 2 (moderate)	
 • Monitor symptoms and provide symptomatic treatment. • Consider consultation with specialists as necessary. • Consider systemic corticosteroids per institutional standard of care.
Grade 3-4 (severe–life-threatening)	
 • Monitor symptoms and provide symptomatic treatment. • Consider consultation with specialists as necessary. • Administer corticosteroids per institutional standard of care. • More potent immunosuppressive therapies should be considered for events not responding to systemic steroids after discussing with the medical monitor. • Study treatment may be permanently discontinued for clinically significant or severe irAEs, or for events where steroid course cannot be tapered below 7.5 mg/day prednisone or equivalent to manage symptoms.

^a Detailed supportive care guidelines for specific irAEs can be found in [Appendix B](#).

5.4.8. Management of Infusion Reactions

[Table 9](#) shows treatment guidelines for subjects who experience an infusion reaction associated with administration of study treatment. Signs and symptoms usually develop during or shortly after drug infusion and generally resolve completely within 24 hours of completion of infusion. Nivolumab and ipilimumab are approved therapies and may have specific infusion reaction management guidelines within their package insert; the treating investigator may use labeled guidance or institutional guidelines for the management of infusion reactions if preferred.

Table 9: Infusion Reaction Treatment Guidelines

CTCAE Grade	Treatment	Premedication at Subsequent Dose Administration
Grade 1: Mild reaction; infusion interruption not indicated; intervention not indicated.	Increase monitoring of vital signs as medically indicated until the subject is deemed medically stable in the opinion of the investigator.	None.
Grade 2: Requires infusion interruption but responds promptly to symptomatic treatment (eg, antihistamines, NSAIDs, narcotics, IV fluids); prophylactic medications indicated for ≤ 24 hours.	
Stop infusion and monitor symptoms. Additional appropriate medical therapy may include but is not limited to the following:
 
 • IV fluids • Antihistamines • NSAIDs • Acetaminophen • Narcotics 
Increase monitoring of vital signs as medically indicated until the subject is deemed medically stable in the opinion of the investigator.
 
If symptoms resolve within 1 hour of stopping drug infusion, the infusion may be restarted at 50% of the original infusion rate. Otherwise, dose administration will be held until symptoms resolve, and the subject should be premedicated for the next scheduled dose.
 
Subjects who develop Grade 2 toxicity despite adequate premedication should be permanently discontinued from further study treatment.
	
Subject may be premedicated 1.5 h (± 30 min) before infusion with the following:
 
 • Diphenhydramine 50 mg orally (or equivalent dose of antihistamine). • Acetaminophen 500-1000 mg orally (or equivalent dose of antipyretic).
Grade 3: Prolonged (ie, not rapidly responsive to symptomatic medication and/or brief interruption of infusion); recurrence of symptoms following initial improvement; hospitalization indicated for other clinical sequelae (eg, renal impairment, pulmonary infiltrates).	
Stop infusion. Additional appropriate medical therapy may include but is not limited to the following:
 
 • IV fluids • Antihistamines • NSAIDs • Acetaminophen • Narcotics • Oxygen • Pressors • Corticosteroids 	No subsequent dose.
Grade 4: Life-threatening; pressor or ventilatory support indicated.	
Increase monitoring of vital signs as medically indicated until the subject is deemed medically stable in the opinion of the investigator.
 
Hospitalization may be indicated.
 
Subject is permanently discontinued from further study treatment.
	

Note: Appropriate resuscitation equipment should be available in the room and a physician readily available during the period of drug administration.

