5.4.9. Criteria for Permanent Discontinuation of Study Drug

The occurrence of unacceptable toxicity not caused by the underlying malignancy will be presumed to be related to study treatment and will require that the study treatment be permanently discontinued. Unacceptable toxicity is defined as follows:

- Grade 4 or life-threatening AEs, except with approval from the medical monitor.
- \geq Grade 2 ocular irAE.
- Occurrence of an AE that is related to treatment, in the judgment of the investigator or the medical monitor, and compromises the subject's ability to continue study-specific procedures or is considered to not be in the subject's best interest.
- Persistent AE requiring a delay of treatment for more than 4 weeks (28 days) unless a greater delay has been approved by the sponsor.

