Dermatitis	
Note: Monitor subjects for signs and symptoms of dermatitis such as rash and pruritus. Unless an alternate etiology has been identified, signs or symptoms of dermatitis should be considered immune-mediated. If there is any bullous formation, the medical monitor should be contacted, and study treatment should be discontinued.
 
For Grade 2 (mild to moderate new symptoms):
 
 • Consider dermatology consult. • Consider symptomatic treatment per institutional standard of care. • Consider moderate-strength topical steroid. • If no improvement of rash/skin lesions occurs within 3 to 5 days or is worsening despite symptomatic treatment and/or use of moderate strength topical steroid, discuss with medical monitor and promptly start systemic steroids. 
For Grade 3 or 4 (severe or new symptoms, new/worsening dermatitis, life threatening):
 
 • Consider dermatology consult. • Promptly initiate empiric IV methylprednisolone or equivalent. • Carefully monitor subject, and institute medical intervention as appropriate for the management of symptoms. • Consider hospitalization. • Once improving, gradually taper steroids over ≥ 4 weeks and consider prophylactic antibiotics, antifungals, and anti-PCP treatment (refer to current NCCN Guidelines for treatment of cancer-related infections [Category 2B recommendation]). • Discuss with medical monitor.

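### After a Grade 3 infusion reaction, Protocol Table 9 forbids further dosing while Table 7 resumes it at the same dose, and nothing says which governs

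*Protocol*

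**What the plan says.** **Infusion reactions (Section 5.4.8, Table 9).**
- Grade 3: the last column reads "No subsequent dose".
- Grade 4: "Subject is permanently discontinued from further study treatment", with no exception. In the text as extracted this sentence sits in the Grade 4 row. The original cell may span Grades 3 and 4, which cannot be seen here.
- Grade 2: "Subjects who develop Grade 2 toxicity despite adequate premedication should be permanently discontinued from further study treatment".
- For nivolumab and ipilimumab, the section adds that "the treating investigator may use labeled guidance or institutional guidelines for the management of infusion reactions if preferred".

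**General rule by grade (Section 5.4.6, Table 7).**
- Grade 1-2: no hold; "Continue treatment at the discretion of the investigator"; the discontinuation column is marked not applicable.
- Grade 3: hold, with the condition for restarting given as "Toxicity resolves to Grade 0-1", then resume all agents at the same dose. Treatment ends only if the toxicity has not resolved within 4 weeks of the last dose (unless the medical monitor approves), or if a resolved Grade 3 event recurs.
- Grade 4: permanent discontinuation unless the medical monitor approves continuation, in which case the dose is unchanged.

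**Unacceptable toxicity (Section 5.4.9).** The list includes "Grade 4 or life-threatening AEs, except with approval from the medical monitor". It names neither infusion reactions nor bullous dermatitis.

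**Dermatitis (Appendix B).** "If there is any bullous formation, the medical monitor should be contacted, and study treatment should be discontinued". No grade is attached.

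**Routing.** Section 5.4.1 advises holding or stopping according to Table 7 for any significant treatment-related event and exempts no event type.

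**The concern.** A site facing a Grade 3 infusion reaction finds two stated rules that point in opposite directions, and no sentence ranks them. This is a conflict between two written instructions, not a missing detail.

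The direct stake is whether a subject who has had a severe reaction is given the drug again. The second stake is the whole regimen: under Section 5.5.1, permanently stopping one study drug stops all of them, so the choice of table also decides whether nivolumab or ipilimumab continues. Two sites could handle the same event differently and both cite the protocol. Counts of discontinuation due to adverse events would then partly reflect which table each site opened.

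**Working it through.** The plan states no figure on this point, so there is nothing to reproduce. The check asks, for each event, whether the action one rule prescribes is an action the other forbids.

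| Event | Event-specific rule | Table 7 | Section 5.4.9 | Result |
|---|---|---|---|---|
| Grade 3 infusion reaction, first occurrence, resolved within 4 weeks | Table 9: no further dose | Resume, same dose | Not listed | Direct conflict |
| Grade 4 infusion reaction | Table 9: stop, no exception | Stop, unless medical monitor approves | Same as Table 7 | Same default; conflict only if the exception is used |
| Grade 2 infusion reaction despite premedication | Table 9: stop permanently | Investigator may continue; discontinuation not applicable | Not listed | Rules not aligned; continuing breaches Table 9 |
| Bullous formation, Grade 1-2 | Appendix B: discontinue | Investigator may continue | Not listed | Rules not aligned |
| Bullous formation, Grade 3 | Appendix B: discontinue | Resume, same dose | Not listed | Conflict |

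**Precedence.** Section 5.4.1 points to Table 7 without a carve-out. Mandatory withdrawal for toxicity in Section 5.5.1 points to Section 5.4.9, not to Table 9 or Appendix B. Section 5.4.9 does carry one event-specific stop (ocular immune-related events of Grade 2 or higher), so the list can hold such rules, but these two events are not on it.

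**Table 7 itself.** The last column of its Grade 4 row covers severe events as well as life-threatening ones, yet the table uses Severe as its label for Grade 3. Read literally, that cell would make a Grade 3 event a permanent stop absent approval, against the Grade 3 row above it. Table 7 therefore needs repair before it can serve as the reference.

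**Exposure still at stake.** Inputs: treatment lasts at most 24 months (Section 4.4); the Amendment 5 summary says enrollment is complete and ongoing subjects have either had more than 15 months of treatment or are in follow-up; cycles are 14 days.
- Time remaining: under 24 − 15 = 9 months.
- Two-weekly doses, at 30.44 days per month: 9 × 30.44 / 14 = 19.6, so at most about 20 per subject, against 0 under Table 9.

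**The case against.** The strongest reply is that Table 9 and Appendix B are event-specific and should be read as overriding a general table. Table 7 is only advised under Section 5.4.1, and Section 5.4.6 leaves interruptions to clinical judgment in consultation with the medical monitor. Table 9 is itself headed as guidelines, and labeled or institutional guidance may replace it for nivolumab and ipilimumab. That reading is natural and many sites would adopt it, but the protocol never states it. The option to use other guidance adds a further possible rule and does not rank the existing ones. The Grade 3 conflict stands.

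Much of the rest is rightly limited. Several stronger readings are tempting, and the documents do not support them:

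- *Section 5.4.9 contains an opposing restart rule.* It does not. It conflicts with Table 9 only through the Grade 4 exception. Otherwise the events are simply not listed, and its bullet on related events that make continuation contrary to the subject's best interest could cover them.
- *Grade 2 is a flat contradiction.* An investigator who stops under Table 9 is using the discretion that Table 7 gives.
- *Appendix B requires permanent discontinuation.* It says discontinued, after contact with the medical monitor, within supportive care guidance that Section 5.4.7 allows labeled or institutional guidance to replace.
- *Table 9 contradicts itself on Grade 2 premedication.* The firmer wording concerns symptoms that have not resolved within 1 hour; the permissive wording covers the whole Grade 2 row. The two can be read together.
- *The dose-escalation counts would shift.* Table 6 already counts nonhematologic toxicity of Grade 3 or higher, with exceptions that do not name infusion reactions, so for Grade 3-4 the choice of table generally changes nothing. For Grade 2 in the concurrent groups, stopping after a Day 15 recurrence first costs the Day 29 dose, outside the 28-day window, unless the Day 15 infusions were left incomplete. In the sequenced groups the window opens at Cycle 3, so a recurrence then could cost a dose inside it, but that needs a particular sequence of events. With enrollment complete, no escalation decision remains open.

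**Conclusion.** The point holds for a Grade 3 infusion reaction: Table 7 prescribes the re-exposure that Table 9 forbids, and no order of precedence is given. The Grade 4 exception, Grade 2 despite premedication and bullous formation are secondary mismatches with the same cause.

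The size is bounded. A reader might take the full 24 months of two-weekly dosing as the exposure at issue. Under the current amendment it is under 9 months, at most about 20 doses, for any subject still on treatment. That bound assumes dosing on schedule to the 24-month limit. The documents give neither an infusion reaction rate nor the number of subjects still being treated, so no expected number of affected subjects can be stated. The conclusion does not depend on how the Grade 3 and 4 cells of Table 9 are merged, because the Grade 3 row carries its own bar on further doses.

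**What to change.** Reconcile Table 7, Table 9, Section 5.4.9 and the dermatitis entry in Appendix B:

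1. State in Table 7 and in Section 5.4.9 which passage governs infusion reactions and which governs bullous dermatitis, including where labeled or institutional guidance fits.
2. State whether the medical monitor exception at Grade 4 applies to infusion reactions.
3. Correct the last cell of the Grade 4 row in Table 7 so that it does not also reach events the table labels as Grade 3.
4. Say whether the Appendix B instruction on bullous formation means permanent discontinuation.

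Which rule is clinically right is for the sponsor's clinical team and is not judged here. The cost is protocol wording or a clarification letter to sites; no new data or analysis is needed.
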